9.4 Secondary Lab Endpoints

CD8+ T cell infiltration:

Given the expected 57% pCR rates, there will be at least 13 responders and 10 non - responders among cases with samples. If the standardized change ((mean value for post-treatment samples – mean value for pre-treatment samples)/sd) is at least 1.1 for responders vs. non-responders, there will be at least 81% power for this comparison. If the post-treatment samples are not available, during-treatment samples will be used. This is based on the two-sample t-test using two-sided type I error rate of 0.1. If normality assumption is not appropriate, Wilcoxon rank sum test will be used during the analysis. Using the median change value, cases will be divided to high and low change groups.

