1.8.2 Secondary

- 1.8.2.1 Patients achieving pCR based on neoadjuvant treatment with a combination of binimetinib and encorafenib will demonstrate a greater decrease in FLT-PET uptake (from baseline to 8 weeks post neoadjuvant treatment initiation) compared to non-pCR patients.
- 1.8.2.2 Lower post-therapy FLT-PET SUVmax is associated with higher likelihood of pCR.
- 1.8.2.3 Change in FLT-PET uptake will correlate with Ki-67 changes in tumor cells. In particular, the change in FLT-PET uptake (from baseline to 8 weeks post neoadjuvant treatment initiation) will directly correlate with the change in early (from baseline to 2 weeks) and post therapy (from baseline to 8 weeks after neoadjuvant treatment initiation) specimen Ki-67 assays.
- 1.8.2.4 Immune effects of treatment with BRAFi + MEKi. CD8+ T cell infiltration at baseline, and/or the change in CD8+ tumor infiltrating lymphocytes (TIL) with treatment early (on treatment biopsy) and late (at resection), in the tumor or tumor bed directly correlates with pCR, disease free survival (DFS) and overall survival (OS).

2. Objectives

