6.1.2 Definitions

Evaluable for Response

Evaluable patients are defined as eligible patients (per Section 3) who receive at least one dose of neoadjuvant therapy with encorafenib and binimatinib and are resectable at enrollment.

- Patients who do receive treatment but demonstrate progression of disease per RECIST and do not proceed to surgery will be classified as pathologic non response (pNR).
- Patients who receive at least one dose of treatment but do not receive surgery for other reasons will be evaluated for radiographic/clinical response.

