9.2 Study Endpoints

Of the 42 patients accrued, we expect at least 39 patients will be evaluable. The main analysis for clinical endpoints will be based on 39 evaluable patients. Based on prior studies, it is not expected that there will be significant issues with disease progression or severe toxicities that interfere with planned surgical resection.

A pCR will be defined as the absence of residual viable melanoma in the resected metastasis site as assessed on local pathology review.

Overall Survival (OS) will be defined as the time from enrollment to death from any cause. Patients who have not died will be censored at the date last known to be alive. Disease-Free Survival (DFS) will be defined as the time from complete surgical resection to disease progression or death (whichever occurs first). Patients who are not eligible for resection will not be included in this analysis. Cases who have not had an event will be censored at the date of last disease assessment documenting the patient was free of progression. Progression will be evaluated based on international criteria proposed by the revised Response Evaluation Criteria in Solid Tumors (RECIST) guideline (version 1.1) as described in Section [6](#). Response will be defined by the RECIST guidelines (version 1.1) as described in Section [6](#). Toxicity will be defined using the CTCAE.

Ki-67 IHC in tumor cells will be graded as a percentage of total number of tumor cells with nuclear staining (to the nearest 10%) over 10 high powered fields (at 20X magnification).

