9.5 Statistical Analysis Plan

Efficacy endpoints will be analyzed in evaluable patients (as defined in Section 9.1. The primary endpoint of pCR rate will be estimated and 90% CI adjusting for the first stage analysis will be provided. OS and DFS distributions will be estimated using the Kaplan-Meier method. Median OS and DFS will be described with 95% confidence intervals. Clinical response rate (RR) (per RECIST 1.1) will be estimated with 95% confidence interval. Clinical data from unevaluable patients will be summarized separately.

Safety analyses will be conducted on all patients who received at least one dose of trial therapy (i.e., treated patients). Adverse events will be graded using the National Cancer Institute (NCI) Common Terminology Criteria for Adverse Events (CTCAE) version 5.0. All treatment-emergent and baseline adverse events and hematological/biochemical toxicities based on laboratory measurements, as well as drug related AEs, will be summarized by NCI CTCAE v. 5.0 worst grade. The incidence of deaths and treatment-emergent serious adverse events (defined as number of patients experiencing the AE divided by all treated patients) will be summarized. Also, the incidence of adverse events leading to discontinuation of investigational product and/or withdrawal from the study will be summarized and listed. Changes in the CD8 T cell infiltration in tumor or tumor bed pre-, during and post- neoadjuvant treatment will be assessed and summarized using the descriptive statistics. The change in CD8+ TIL between pre-and post-treatment will be compared among patients achieving a pCR vs. no pCR using the Wilcoxon rank sum test. The concordance of pCR assessed based on local review vs. central pathology review will be evaluated. Kendall's Tau test will be used for this comparison.

In the event of missing data, it will be assumed that the data will be missing at random and no imputation will be performed.

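### Sections 9.4 and 9.5 give different sample rules and different tests for the comparison of CD8 change by pCR status

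*Combined protocol and SAP*

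**What the plan says.** Section 9.4 (Secondary Lab Endpoints) expects at least 13 responders and 10 non-responders with samples. It claims at least 81% power for a standardized difference of 1.1. On the test it says "This is based on the two-sample t-test using two-sided type I error rate of 0.1", followed by "If normality assumption is not appropriate, Wilcoxon rank sum test will be used during the analysis". On the sample it says "If the post-treatment samples are not available, during-treatment samples will be used".

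Section 9.5 (Statistical Analysis Plan) covers the same comparison. The change in CD8+ TIL "between pre-and post-treatment will be compared among patients achieving a pCR vs. no pCR using the Wilcoxon rank sum test". It mentions no t-test, no normality condition and no substitute sample. It separately says that CD8 changes "pre-, during and post- neoadjuvant treatment will be assessed and summarized using the descriptive statistics". It closes by assuming that missing data are missing at random and by ruling out imputation.

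Three other places bear on this:
- Hypothesis 1.8.2.4 concerns baseline CD8 and/or its change "with treatment early (on treatment biopsy) and late (at resection), in the tumor or tumor bed directly correlates with pCR", so early and late change are listed as separate quantities.
- Section 9.2 ties the outcome to surgical tissue: "A pCR will be defined as the absence of residual viable melanoma in the resected metastasis site".
- Section 9.7.3.2 notes that the week-2 biopsy is optional and that few patients are expected to have one.

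**The concern.** Two analysts following this plan could report different results for one endpoint. One would put a week-2 value in place of a missing resection value, check normality and perhaps run a t-test. The other would use only patients with a resection sample and run Wilcoxon. Section 9.4 gives no criterion for judging normality, so its choice of test would be made after seeing the data.

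The substitution also changes what is estimated. A change over about 2 weeks of treatment and a change over about 8 weeks are different biological quantities. Pooling them answers neither part of hypothesis 1.8.2.4 cleanly. Who receives the substitute may also depend on the outcome, because a patient without surgery has no resection sample and cannot have a pCR.

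**Working it through.** **1. The plan's own figure.** Inputs from Section 9.4: n1 = 13, n2 = 10, d = 1.1 SD, two-sided alpha 0.10, two-sample t-test. The group sizes fit 23 patients at a 57% pCR rate: 23 × 0.57 = 13.1 and 23 × 0.43 = 9.9.

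- Degrees of freedom: 13 + 10 − 2 = 21.
- Non-centrality: d × √(n1·n2/(n1+n2)) = 1.1 × √(130/23) = 2.615.
- Non-central t power: **81.2%**. The stated 81% reproduces.

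**2. The test named in 9.5.** Same sizes, effect and alpha, by simulation. The documents give no distribution, so each one here is an assumption.

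| Test | Data | Power |
|---|---|---|
| t-test | normal | 81.2% |
| Wilcoxon, exact (U ≤ 37, size 0.0883) | normal | 77.3% |
| Wilcoxon, uncorrected normal approximation (size 0.101) | normal | 79.3% |
| Wilcoxon, exact | t with 5 df | 84% |
| Wilcoxon, exact | Laplace | 85% |
| Wilcoxon, exact | exponential | 89% |

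In the three non-normal cases the t-test has about 82%. Under normality the Wilcoxon shortfall is 81.2 − 79.3 = 1.9 to 81.2 − 77.3 = 3.9 points. Part of the exact-test shortfall comes from discreteness, since its size is 0.088 and not 0.10. One more patient per group (14 v 11) brings exact Wilcoxon to 81.7%, and Section 9.4 gives 13 and 10 as minimums.

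**3. Where a substitution can fall.**
- *No surgery.* pCR requires resected tissue (9.2), so this patient cannot be in the pCR group. Section 6.1.2 classes RECIST progressors without surgery as pathologic non-response and sends other unoperated patients to radiographic/clinical assessment. Under the pCR v no-pCR contrast in 9.5, the latter are most naturally read as no pCR.
- *Surgery, but no usable or consented tissue.* This can occur in either group. Section 11.2 asks for sections of viable tumor, which a pCR specimen lacks by definition. The objectives allow measurement in the tumor bed, so such a specimen is not necessarily unusable.

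**4. What one substitution could do.** Illustration: exact Wilcoxon, normal data, 13 v 10, one of the 10 non-responders carrying a week-2 value. The shift between week-2 and resection change is assumed; the documents give none.

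| Shift of that value | 0.5 SD | 1.0 SD | 1.5 SD |
|---|---|---|---|
| Toward responders: power | 73.4% | 68.8% | 64.3% |
| Away from responders: power | 80.1% | 81.9% | 83.0% |

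The null rejection rate is 8.8–9.0%, against 8.8% with no substitution. The table covers a non-responder only. A substituted responder works the same way in mirror image: a shift toward the non-responders lowers power and a shift away raises it.

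**5. Cost of not substituting.** Losing one non-responder (13 v 9):
- t-test: 81.2% to 79.0%, a loss of 2.2 points.
- Uncorrected Wilcoxon: about 79% to about 76%, a loss of about 3 points.
- Exact Wilcoxon: 77.3% to 75.9%, a loss of 1.4 points. This is smaller because the exact size rises from 0.088 to 0.096.

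If five patients were lost (10 v 8, an assumed number), the t-test has 71.7% and exact Wilcoxon 66.1%.

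**The case against.** Powering on a t-test and analysing by ranks is common practice. Section 9.4 can be read as the power basis and 9.5 as the analysis rule, with 9.5 settling in favour of Wilcoxon. That would dispose of the test question, except that 9.4 states when Wilcoxon is to be used in the analysis, and that is itself an analysis rule. The ambiguity is mild but real.

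On the sample, a specific rule in 9.4 that 9.5 does not repeat is not by itself a contradiction. The closing sentence of 9.5 on imputation makes it one only if using an observed week-2 value counts as imputing the resection value, which is arguable. Even if it does not count, 9.5 describes a pre- to post-treatment contrast that a week-2 value does not satisfy.

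Substitutions may also be few. Section 9.1 expects failure to reach surgery to be very low, and few week-2 biopsies are expected. The first point covers only missing surgery, not missing tissue, but rarity does limit the consequences.

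A reader might infer more than the documents support:
- *That the 81% is wrong.* It is right for the test named beside it.
- *That Wilcoxon leaves the comparison underpowered.* The 77–79% holds under normality, the very case in which 9.4 would keep the t-test. With the heavier-tailed or skewed data tried above, Wilcoxon does better than 81%.
- *That the substitution biases the result in one known direction or inflates false positives.* Substitutes can fall in either group and shift either way, and one substituted non-responder leaves the null rejection rate below 0.10.

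**Conclusion.** The inconsistency stands as a low-priority drafting point. The plan gives two sample rules and two test rules for one secondary laboratory endpoint, and one sample rule mixes early with late change. Under normal data, the choice of test is worth about 2 to 4 points of power at the planned sizes. The effect of substitution depends on the number of substitutes, their group and the gap between week-2 and resection change, none of which the documents give; it can go either way. The primary pCR analysis and the stated 81% for the t-test are unaffected.

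**What to change.** Amend Sections 9.4 and 9.5 so that they agree, before CD8 data are linked to pCR status. After that, choosing between them would depend on the data.

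- **Main comparison:** baseline-to-resection change by pCR status, in patients with both samples and without substitution. This is consistent with 9.5.
- **Week-2 data:** report baseline-to-week-2 change separately. Section 9.5 already summarises during-treatment CD8, so nothing is discarded.
- **Substituted version:** at most a labelled sensitivity analysis, with the number of substitutions shown by pCR status.
- **Test:** name one in both sections. If Wilcoxon, state the version, note that 81% is the t-test figure, and give about 77% (exact) to 79% (uncorrected) under normality. If the t-test, keep 81% and amend 9.5.

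The cost is a wording change to the combined document. The downside is roughly 1 to 3 points of power for each patient who leaves the late-change comparison. That comparison then describes only patients who had surgery, which should be stated with the result.

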9.5 Statistical Analysis Plan

Efficacy endpoints will be analyzed in evaluable patients (as defined in Section 9.1. The primary endpoint of pCR rate will be estimated and 90% CI adjusting for the first stage analysis will be provided. OS and DFS distributions will be estimated using the Kaplan-Meier method. Median OS and DFS will be described with 95% confidence intervals. Clinical response rate (RR) (per RECIST 1.1) will be estimated with 95% confidence interval. Clinical data from unevaluable patients will be summarized separately.

Safety analyses will be conducted on all patients who received at least one dose of trial therapy (i.e., treated patients). Adverse events will be graded using the National Cancer Institute (NCI) Common Terminology Criteria for Adverse Events (CTCAE) version 5.0. All treatment-emergent and baseline adverse events and hematological/biochemical toxicities based on laboratory measurements, as well as drug related AEs, will be summarized by NCI CTCAE v. 5.0 worst grade. The incidence of deaths and treatment-emergent serious adverse events (defined as number of patients experiencing the AE divided by all treated patients) will be summarized. Also, the incidence of adverse events leading to discontinuation of investigational product and/or withdrawal from the study will be summarized and listed. Changes in the CD8 T cell infiltration in tumor or tumor bed pre-, during and post- neoadjuvant treatment will be assessed and summarized using the descriptive statistics. The change in CD8+ TIL between pre-and post-treatment will be compared among patients achieving a pCR vs. no pCR using the Wilcoxon rank sum test. The concordance of pCR assessed based on local review vs. central pathology review will be evaluated. Kendall's Tau test will be used for this comparison.

In the event of missing data, it will be assumed that the data will be missing at random and no imputation will be performed.

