1.7 Trial Rationale

This trial is a single arm phase 2 study to investigate encorafenib, a selective BRAF inhibitor, in combination with binimetinib, a MEK inhibitor, in the neoadjuvant treatment of resectable clinically or radiographically-detected stage IIIB/C/D melanoma. The treatment period planned will be a total of one year, with 8 weeks of therapy prior to planned surgery followed by 44 weeks of combination treatment postoperatively. Responses to combination BRAFi/MEKi usually occur within 2 months, hence an 8-week treatment period was chosen to evaluate response as well as not to delay definitive surgical resection. The Columbus trial of encorafenib with binimetinib yielded favorable response and safety data in advanced metastatic melanoma. [Dummer, Lancet Oncol, 2018] The planned clinical primary end-point is pathologic complete response (pCR) as determined by local assessment of surgical pathologic specimens and radiology studies. Central pathology review of the pre-study biopsy and post-neoadjuvant treatment surgical specimens will also be accomplished retrospectively, as has been customary for ECOG-ACRIN Melanoma Committee studies. This trial will evaluate the benefit of these agents, the role of pathologic CR (pCR) as an endpoint, and the toxicity profile of encorafenib with binimetinib in this setting and population. It is possible that the toxicity profile may be distinct from that seen with other BRAF/MEKi doublets.

Additional hypotheses center upon translational components, which are seeking markers of clinical response and/or early indicators of response (or resistance). In all cases, the relationships of these components to each other will also be explored, e.g., whether changes in measures of melanoma immunity correlate with changes in imaging. This trial will include a radiologic key secondary endpoint with a molecular imaging marker FLT PET, designed to test an early

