2.3 Correlative Science Objectives

2.3.1 To evaluate CD8+ T cell infiltration and Ki-67 status in tumor or tumor bed pre, during, and post neoadjuvant treatment and the change in CD8+ TIL with neoadjuvant treatment and correlate with clinical response.

2.3.2 To compare local review for pathologic response with central pathology review.

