6.1.5 Response Criteria

6.1.5.1 Pathologic Response Rate (pCR)

Pathologic complete response (pCR) is defined as the absence of residual melanoma in resected tissue as assessed on local pathology review. These will have central review retrospectively.

- **Pathologic complete response (pCR)**
 - Complete absence of viable tumor in the treated tumor bed
- **Major PR**
 - $\leq 10\%$ of viable tumor in the treated tumor bed
- **Partial pathologic response (pPR)**
 - Less than or equal to 50% of the treated tumor bed is occupied by viable tumor cells
- **Pathologic non-response (pNR)**
 - Greater than 50% of the treated tumor bed is occupied by viable tumor cells

Pathologic Response	Remarks
pCR	Complete absence of viable tumor in the treated tumor bed
Major PR	$\leq 10\%$ of viable tumor in the treated tumor bed
pPR	Less than or equal to 50% of the treated tumor bed is occupied by viable tumor cells
pNR	Great than 50% of the treated tumor bed is occupied by viable tumor cells
	Patients that demonstrate objective RECIST progression, they will be classified at pathologic NR

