9.1 Study Design and Objectives

In this phase II study, patients with resectable locoregional metastases from cutaneous or unknown primary melanoma (Stages III N1B/C/D) will be enrolled. The primary objective is to evaluate the pCR rate for the neoadjuvant combination of encorafenib and binimatinib. It is hypothesized that this combination of treatment will yield at least 57% pCR rate. Simon's two-stage design will be used, enrolling with up to 42 patients (for 39 evaluable).

Evaluable patients are defined as eligible patients (per Section [3](#)) who receive at least one dose of neoadjuvant therapy with encorafenib and binimatinib and are resectable at enrollment. The likelihood of progression, delay in resection or failure to proceed to surgery during the neoadjuvant period is expected to be very low. Therefore, we expect at least 39 out of 42 patients will be evaluable.

All patients who receive at least one dose of neoadjuvant therapy will be included in the 15 patient-cohort that will trigger the interim analysis.

Secondary clinical endpoints include: i) to evaluate clinical response rate (RR), DFS, OS, ii) to assess correlation of pCR with RR, DFS, OS, iii) to assess safety and toxicity iv) to evaluate CD8+ T cell infiltration in tumor or tumor bed pre, during and post neoadjuvant treatment and the change in CD8+ TIL with neoadjuvant treatment and correlate with clinical response, and v) to compare local review for pathologic response with central pathology review. Secondary imaging endpoints are addressed in Section [9.7](#).

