9.3 Sample Size Considerations and Monitoring Plan

A Simon's optimal two-stage design will be used to allow for an interim analysis for futility. Accrual will be held during the interim analysis. Fifteen (for 14 evaluable) subjects will be enrolled and pCR will be assessed. If 5 or fewer subjects achieve a pCR, the trial will be stopped for futility. If greater than 5 subjects achieve a pCR, then the trial will enroll an additional 27 (for 25 evaluable) patients. If 18 or more subjects out of 39 total evaluable subjects achieve a pCR the study will be considered 'positive'. The study was designed to evaluate the pCR rate improving from 33% to 57%. This design provides 87% power with approximately one-sided type I error rate of 0.05 for the primary endpoint.

The hypothesis states that encorafenib with binimatinib will yield a pCR rate of 57%. The baseline pCR rate of 33% was estimated from published values as summarized in Table 1 in Section [1](#) and is thus the null pCR rate.

We anticipate an average accrual of 1-3 patients per month. The first stage analysis will occur when the first 15 patients have a pCR assessed. Under the null pCR rate of 33%, there is 70% chance of stopping the study after the first stage evaluation. Adverse events will be closely monitored during the study.

Interim safety analyses based on the first 15 patients will evaluate:

- Proportion of patients who develop progressive disease per RECIST 1.1 before surgery but proceed with surgical resection
- Proportion of patients who develop progressive disease per RECIST 1.1 before surgery and are unresectable
- Proportion of patients who develop toxicities that delay or prohibit surgery
- Surgical complications as defined by the operating surgeon as being related to surgery or oral therapy, at any point during follow up

We anticipate that the proportion of patients who experience any of the event listed in i) -iv) will be less than 15%. If at least one patient (out of 15 patients) experiences any of the event listed in i) - iv), the proposed treatment will be considered unsafe and the result will be discussed with the ECOG-ACRIN DSMC. The probability of observing at least one patient with the event in i) ii), iii) or iv) is 0.794 if the true event rate is 10% and is 0.913 if the true event rate is 15%.

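### Local versus central pCR concordance is tested only with Kendall's tau, which tests for association and shows neither how well the two reads agree nor which one calls pCR more often

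*Combined protocol and SAP*

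**What the plan says.** Objective 2.3.2 is "To compare local review for pathologic response with central pathology review". Section 9.1 repeats it as item (v) of the secondary clinical endpoints. The analysis is in Section 9.5: "The concordance of pCR assessed based on local review vs. central pathology review will be evaluated", followed by Kendall's "Tau test will be used for this comparison".

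Neither Section 9.5 nor any other section names a cross-tabulation, percent agreement, kappa, confidence interval, paired comparison of pCR rates, alpha level or acceptable level of agreement for this comparison.

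The variable in Section 9.5 is pCR, a yes/no outcome. Section 9.2 ties it to the local read: "A pCR will be defined as the absence of residual viable melanoma in the resected metastasis site as assessed on local pathology review". The success rule in Section 9.3 ("If 18 or more subjects out of 39 total evaluable subjects achieve a pCR") therefore rests on local review. On central review, Section 1.7 says: "Central pathology review of the pre-study biopsy and post-neoadjuvant treatment surgical specimens will also be accomplished retrospectively". Section 6.1.5.1 also defines a four-level response: pCR, major PR, pPR and pNR.

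**The concern.** Objective 2.3.2 raises two questions: how often the two reviews agree beyond chance, and whether one is systematically more generous in calling pCR. The p-value from a tau test answers neither. It asks whether the reads are unrelated, which nobody would expect of two reads of the same resection specimen. A small p-value could then be reported as concordance when agreement is mediocre or when central review finds clearly fewer pCRs.

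This matters because the trial has a single arm and a locally read primary endpoint. The comparison with central review is the plan's only check on that read.

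**Working it through.** **Inputs.** 39 evaluable patients (Sections 9.1 to 9.3) and a hypothesised pCR rate of 57% (Section 9.1), so about 0.57 × 39 ≈ 22 local pCRs. The plan gives no power, threshold or discordance rate for this analysis, so there is no stated figure to reproduce. The cell counts below are assumed, and two-sided 0.05 is assumed unless stated.

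**Formulas.** Cells: a = both pCR, b = local only, c = central only, d = neither; n = a + b + c + d.
- For a 2x2 table tau-b equals phi = (ad − bc) / √[(a+b)(c+d)(a+c)(b+d)], with test statistic z = phi × √(n − 1).
- Agreement = (a + d)/n.
- Kappa = (agreement − chance) / (1 − chance), where chance = [(a+b)(a+c) + (c+d)(b+d)] / n².
- Paired difference = (b − c)/n.
- Exact McNemar uses b and c only.

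**Case 1: equal rates, 16/6/6/11 (both readers 22 pCR).**
- phi = (16×11 − 6×6)/(22×17) = 140/374 = 0.374; z = 0.374 × √38 = 2.31; p = 0.021.
- Agreement = 27/39 = 69% (exact 95% CI 52 to 83).
- Chance = (22×22 + 17×17)/1521 = 0.508; kappa = (0.692 − 0.508)/0.492 = 0.37 (0.08 to 0.67). This equals tau-b, as it must when both readers have the same pCR rate.
- McNemar p = 1.0.

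**Case 2: local calls more pCRs, 14/8/0/17 (local 22, central 14).**
- phi = 14×17/√(22×17×14×25) = 238/361.8 = 0.658; z = 4.06; p = 0.00005.
- Agreement = 31/39 = 79% (64 to 91).
- Chance = (22×14 + 17×25)/1521 = 0.482; kappa = 0.60 (0.38 to 0.83).
- Paired difference = 8/39 = 20.5 points (Newcombe 95% CI 6.7 to 32.8); McNemar p = 2 × 0.5⁸ = 0.008.
- Tau would be reported as highly significant although central review finds 8 fewer pCRs and its count falls below 18.

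**Case 3: extreme over-calling, 6/16/0/17 (local 22, central 6).** tau-b 0.375, p = 0.021; agreement 23/39 = 59%; kappa 0.25; McNemar p = 0.00003. Cases 1 and 3 share a tau p-value of 0.021 but describe very different disagreements.

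**How often the test rejects.** Simulation with n = 39, both readers at 57% pCR and 40,000 trials per setting. Expected agreement is 1 − 2 × 0.57 × 0.43 × (1 − kappa).

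| True kappa | Expected agreement | Rejects, two-sided 0.05 | Rejects, one-sided 0.05 |
|---|---|---|---|
| 0.3 | 66% | 47% | 59% |
| 0.4 | 71% | 72% | 82% |
| 0.5 | 75% | 90% | 95% |

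**If the four ordered categories are compared instead.** Rows local, columns central, in the order pCR, major PR, pPR, pNR: [14,8,0,0], [0,2,4,0], [0,0,3,3], [0,0,0,5]. Central is one category lower in 8 + 4 + 3 = 15 of 39. Tau-b is 0.84 (p = 2 × 10⁻⁹), but exact-category agreement is 24/39 = 62% and linear-weighted kappa is 0.69 (bootstrap 95% CI 0.53 to 0.81). Here the coefficient, and not only its p-value, hides a systematic shift.

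**The case against.** **The wording does not exclude more.** Section 9.5 says concordance will be evaluated and does not rule out a table or the coefficient. That is true, but it commits to neither, and a measure chosen after the reads are seen is not pre-specified.

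**The coefficient carries most of the information on agreement.** For binary pCR this largely stands. Tau-b equals kappa when the readers' rates match and stays close when they differ mildly: an assumed 19/3/1/16 table gives 0.798 against 0.794. The gap widens as the rates separate (0.66 against 0.60 in case 2, 0.375 against 0.25 in case 3), and tau never shows which reader calls more pCRs. The fault is reliance on the test, not that tau-b is meaningless.

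**The ordered-scale case is hypothetical, and weighted kappa can also look high.** Section 9.5 says pCR, so the four-level case arises only under the broader wording of 2.3.2 and 9.1. On the four-level table above, quadratic-weighted kappa is 0.86, slightly above tau-b. This is why the weights must be fixed in advance.

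**The tables are invented and the sample is small.** Both points stand. Thirty-nine pairs is an upper planning figure: Section 6.1.2 classifies patients who progress and have no surgery as pNR without a specimen, and others may not be resected. McNemar is also weak at this size; four discordant reads all in one direction give p = 2 × 0.5⁴ = 0.125. The confidence intervals should therefore carry the interpretation.

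**It is only a secondary analysis.** That is correct, and it limits the weight of the point.

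**Conclusion.** The concern holds. The one method named for local-central concordance tests a null hypothesis that does not bear on objective 2.3.2. With 39 pairs it can reach p = 0.021 at 69% agreement and kappa 0.37, and p = 0.00005 when the two pCR rates differ by 20.5 points. These sizes rest on assumed tables and an assumed two-sided 0.05; the conclusion about what the test measures does not.

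The primary endpoint, the 18-of-39 rule, its alpha and its power are untouched. This should be corrected, but it does not threaten the trial's main conclusion.

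**What to change.** In Section 9.5 replace the tau test with:

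- the local-by-central 2x2 table and the number of paired reads;
- percent agreement and Cohen's kappa, each with a 95% CI;
- discordant counts by direction, with the paired difference in pCR rates (95% CI) and an exact McNemar test.

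State whether the comparison is of pCR alone or of all four categories. If the latter, add the 4x4 table and a weighted kappa with the weights named now. Linear weights register a one-category shift much more than quadratic ones do (0.69 against 0.86 on the same table).

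Optionally, as a labelled sensitivity analysis, report the pCR rate on central review with its actual denominator. List separately the patients with no resection and those whose tissue was not submitted or not readable, and set the result against 18 of 39 only if all 39 are accounted for.

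The cost is one paragraph and one table. Sections 7.2 and 10.1 already make baseline and surgical tissue mandatory for central review, so sample size, conduct and data collection do not change.
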